#### Study Schema:

Baseline Measure	Skin-sparing or Nipple-sparing mastectomy	Outcome Measure
Stratify by:		
1. Site	Acellular dermal matrix assisted one-stage implant reconstruction	1. Breast Q ©
UHN WCH VGH		2. EQ-5D
2. Laterality		3. Complications
Unilateral Bilateral		4. Aesthetics
	Two-stage tissue expander/implant reconstruction	5. Cost-effectiveness

The **primary outcome** evaluated will be **patient-reported satisfaction and quality of life** associated with the use of ADM in one-stage immediate prosthetic breast reconstruction following skin-sparing or nipple-sparing mastectomy. Patient-reported satisfaction and quality of life will be measured using the Breast Q© questionnaire. These questionnaires will be administered to patients prior to mastectomy, at two weeks following the mastectomy and immediate reconstruction, 6 months and one year (+/- 1 month) following completion of reconstruction. It is hypothesized that ADM assisted one-stage prosthetic breast reconstruction will be associated with improvement in patient-reported satisfaction and quality of life compared to the conventional two-stage TE/implant reconstruction.

The **secondary outcomes** will include **short and long-term complication rates**, overall **aesthetic outcome** including capsular contracture formation at six month and one-year following completion of the reconstruction, and a **cost effectiveness analysis (CEA)**. For the cost-effectiveness analysis, person-level cost and effect data will be collected throughout the study. The cost data will come from hospital cost accounting systems and patient reports. The patient outcome data will be collected at months 6 and 12 months post-mastectomy by the Breast Q© and EQ-5D. The primary measure of effectiveness will be the global Breast Q© score and the secondary measure will be quality adjusted life years (QALY) as measured by the EQ-5D. It is hypothesized that the short- and long-term complication rates will be comparable between the two study arms, while the overall aesthetic outcome will be superior with less severe capsular contracture in the ADM assisted one-stage than the two-stage TE/implant reconstruction. Lastly, we hypothesize ADM assisted one-stage implant reconstruction will be the more cost effectiveness method of implant reconstruction following mastectomy than the standard two-stage TE/I method.

Timing of Questionnaires

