##### ***Randomization***

Randomization will occur in during the pre-operative consult although the participant's final eligibility will be determined during surgery (see section on Eligibility). Patients will be randomized to undergo either ADM assisted one-stage reconstruction or two-stage reconstruction with TE placement without the use of ADM. The randomization allocation list will be developed by the Department of Epidemiology and Biostatistics at the University Health Network Research Institute. Sequentially numbered and sealed envelopes containing the treatment assignments will be prepared and given to the study coordinator in charge of the study site. Each envelope will contain two identical datasheets with the patient's name, medical record number and treatment assignment. One sheet will be returned to the study coordinator and the other sheet will be placed in the patient's chart.

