#### **iib-6. Postoperative treatment**

In **Group B**, at 2 weeks after the operation, office expansion will be undertaken and continued on a biweekly basis. With each expansion, the endpoint of expansion will include either: (1) persistent blanching or congestion of the mastectomy flap; or, (2) patient discomfort. The expansion phase will be considered complete once the volume in the expanded breast represents 100 percent (+/- 20 percent) of the recommended expander volume. If required, postoperative chemotherapy is generally given during the expansion period. Expanders are then exchanged approximately between 4-6 weeks following the completion of chemotherapy or 3-6 months following completion of inflation. All patients in group B will undergo a second exchange procedure at which time the expander is removed and a permanent implant is placed. In all instances, the permanent implant to be used will be anatomic cohesive silicone gel implants (Style 410, Allergan, Santa Barbara, CA).

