2. **long-term aesthetic result**: Evaluation of the overall aesthetic result and capsular contracture grade will be performed at six months and one year following the completion of reconstruction. A routine physical examination will be performed by the attending surgeon and photographic documentation (5 standardized photographs) of the reconstruction will be obtained at the six month and one-year follow-up visit. A panel of three independent, blinded observers will subsequently evaluate the overall aesthetic result using the three-point, five item, Breast Aesthetic Score described by Lowery with the use of photographic documentation. Capsular contracture will be graded by the examining physician and will be graded using the Modified Baker Scale for Reconstructed Breasts, which is widely accepted to be the gold-standard measure of capsular contracture grade.
3. **cost-effectiveness**: Costs and effects will be simultaneously analyzed by collecting person-level cost and effect data. The cost data will come from hospital cost accounting systems and patient reports. The patient outcome data will be collected at months 6 and 12 months post-mastectomy by Breast Q $\circ$

and EQ-5D. The frequently used generic HRQoL instrument EQ-5D will be piggy-backed to the Breast QoL at the 2 post-mastectomy time-points to generate a utility value for current health. The primary measure of effectiveness will be the Breast Q score and the secondary measure will be quality adjusted life years (QALY) as measured by the EQ-5D (APPENDIX 6)

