#### ***ii) Secondary Analysis***

Short-term (intra-operative and early post-operative) and long-term postoperative complications will be documented and collected prospectively at each site by the study coordinator. Group comparisons will be performed using the Pearson's chi-square test or binomial test, where appropriate for these categorical variables. Repeated measure analysis will be used for Breast Aesthetic Score at 6 and 12 months post mastectomy. The Modified Baker Scale for capsular contracture results in an ordinal variable which will be compared using the Pearson's chi-square test.

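### Capsular contracture has its own directional hypothesis and test but no stated blinding; the plan should say that the blinded photographic score alone decides the aesthetic claim.

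*Combined protocol and SAP*

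**What the plan says.** Section iib-8, secondary outcome 2, sets two evaluations at six months and one year after reconstruction is complete.

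- **Overall aesthetic result.** Standardised photographs are scored on the Breast Aesthetic Score: "A panel of three independent, blinded observers will subsequently evaluate the overall aesthetic result".
- **Capsular contracture.** The Modified Baker Scale is used, and "Capsular contracture will be graded by the examining physician". The examination at these visits is assigned in the same paragraph: "A routine physical examination will be performed by the attending surgeon". No blinding is stated for this grade, and no independent or second grader is provided.

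The text under Study Schema describes the aesthetic outcome as "including capsular contracture formation at six month and one-year following completion of the reconstruction" and predicts that "the overall aesthetic outcome will be superior with less severe capsular contracture in the ADM assisted one-stage" arm. Section 9c ii analyses the two measures separately: repeated measures for the Breast Aesthetic Score, and for the Baker grade, which "results in an ordinal variable which will be compared using the" Pearson chi-square test. Secondary objective 2 in section i concerns the overall aesthetic outcome only and does not mention contracture.

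**The concern.** The Baker grade is an ordinal clinical judgement made at a physical examination. If the person making it knows the arm and shares the trial's expectation, borderline cases can be graded lower in the ADM arm. That error follows treatment, so the covariate adjustment in iib-7 and 9a cannot remove it, and neither can the chi-square test.

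The plan protected one subjective rating from this and left its companion in the same paragraph unprotected. It also does not say how the two combine. If the blinded score shows no difference and the Baker grade favours ADM, nothing in the plan says what may be concluded about aesthetics or how much weight the contracture result should carry.

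**Working it through.** **1. Who grades, and do they know the arm?** Two links are inferred, not stated.

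- *The examining physician is the attending surgeon.* The paragraph in iib-8 names no other examiner for these visits.
- *That surgeon ordinarily knows the arm.* Under Randomization, "One sheet will be returned to the study coordinator and the other sheet will be placed in" the patient's chart. The operations differ: Group A has an ADM pocket with two drains, Group B a muscle-fascial pocket with one. Only Group B has office expansions, and under iib-6 "All patients in group B will undergo a second exchange procedure at which time the expander is removed".

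**2. Which measure decides the aesthetic hypothesis?**

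| Place | Is contracture part of the aesthetic outcome? |
|---|---|
| Section i, secondary objective 2 | Not mentioned |
| Study Schema text | Included, with a direction |
| iib-8, outcome 2 | Listed beside the overall result, with a different assessor |
| 9c ii | Separate test |

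No section ranks the two measures or states a decision rule.

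**3. The plan's own figure.** Section iib-10 sizes the trial on the Breast Q only (difference 10, SD 20, alpha 0.05, power 85%). With two-sided alpha:

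n per arm = 2 × (1.960 + 1.036)² × 20² / 10² = 2 × 8.98 × 4 = 71.8, so 72.

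This reproduces the stated 72. There is no rate, effect size or power for contracture, so the size of any bias cannot be derived from the documents.

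**4. Illustration, on assumptions.** 72 women per arm. The grade is cut at one threshold, and the true proportion p reaching it is the same in both arms. A fraction m of one-stage contractures is recorded below the threshold, so the recorded one-stage rate is p(1 − m). The test is the uncorrected Pearson chi-square at 0.05:

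z = (x₁ − x₂)/72 ÷ √[p̄(1 − p̄) × 2/72], with p̄ = (x₁ + x₂)/144; reject if |z| > 1.96.

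The rejection probability is the sum, over all pairs (x₁, x₂), of the product of the two binomial probabilities for the pairs that reject.

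| True rate p | m = 0 | m = 12.5% | m = 25% | m = 37.5% | Women moved at m = 25% (72 × p × 0.25) |
|---|---|---|---|---|---|
| 5% | 5% | 5% | 6% | 8% | 0.9 |
| 10% | 5% | 6% | 8% | 13% | 1.8 |
| 20% | 5% | 7% | 12.5% | 23% | 3.6 |
| 40% | 5% | 9% | 24% | 49% | 7.2 |

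The inflation depends on both unknowns and is slight when contracture is uncommon.

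**5. Limits of the illustration.** Section 9c ii applies Pearson's test to the ordinal grade, not to a dichotomy. The plan does not say whether the unit is the woman or the breast. Bilateral reconstruction was common: iia-3 shows 10 + 8 + 8 + 6 = 32 of 51 randomised patients.

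**The case against.** The strongest reply is that the overall aesthetic result is already protected. Section i states the aesthetic hypothesis without contracture, iib-8 gives the overall result to the blinded panel, and 9c ii tests the two measures apart. Only the Study Schema text joins them, and there superiority is predicted together with less contracture, not by either one. This stands. A reader might infer that the plan lets the Baker grade alone establish superior aesthetics; no section says so. What remains is that no section rules it out, and that contracture has its own hypothesis and test without stated blinding.

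A second inference is that contracture could easily be graded blind, because both arms end with the same type of implant. The documents do not support that. The pocket differs, the number of operations differs, the patient knows which she had, and iib-1 (Innovation) reports that ADM alters lower-pole shape and rippling. Keeping the chart closed would remove only one source of knowledge. Nor do the documents show that a second surgeon could grade without extra resources: iia-2 gives a surgeon count for the Vancouver site only.

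Third, this is one component of a secondary outcome, and the primary outcome is the patient-reported Breast Q. That is fair and limits the weight of the point. It does not answer it, since contracture is named in a directional hypothesis.

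**Conclusion.** The concern holds in limited form. A secondary outcome with a directional hypothesis and its own test is graded without stated blinding by someone who will ordinarily know the arm, and the plan does not say which measure decides the aesthetic hypothesis. That the grader knows the arm is a strong inference from the design, not a statement in the text.

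Under the assumptions above, under-grading a quarter of one-stage contractures gives a false-positive rate of about 6% to 24% for true rates of 5% to 40%, in place of about 5%. A reader might take the 49% cell as the expected harm. It needs both a 40% contracture rate and more than a third of one-stage contractures under-graded, and the documents support neither figure. They do not show that biased grading has occurred. The primary analysis and the blinded photographic score are unaffected.

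**What to change.** In iib-8 (outcome 2) and 9c ii, state that:

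1. the claim of superior aesthetic outcome rests on the blinded panel's Breast Aesthetic Score alone;
2. the Modified Baker grade is reported as an unblinded, supportive outcome, which cannot by itself establish superior aesthetics or less contracture with ADM.

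Bring the Study Schema text into line with this. The wording should be settled before these outcomes are compared by arm. The interim results reported in iia-3 cover complications and costs, not contracture or the aesthetic score.

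The cost is a few sentences, with no added visit, assessor or patient. It can be applied even if some gradings have already been made. The downside is that the contracture hypothesis becomes supportive. The change does not remove bias from the grade; it limits what a biased grade can be used to claim.

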## **iib-9. Data Analysis**

### **9a. Confounders and their Measurements**

Critical covariates will be identified at baseline and documented in the demographic assessment forms. (APPENDIX 7) Analysis will be adjusted for the confounders using both stratification and controlled for during repeated measures analysis using SPSS v18.

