## **iib-8. Outcomes and their measurements**

### **Primary Outcome: *Patient-Reported Satisfaction and Quality of Life***

Patient satisfaction and quality of life will be measured using the Breast Q $\circ$  as a self-administered questionnaire. The Breast Q $\circ$  has 2 subscales that examine the two different domains: satisfaction and psychosocial function. The scores generated for each subscale will be transformed on a scale from 0-100, lowest to highest summary scores respectively. Scale validity and reliability are supported by the high Cronbach's alpha coefficient (>0.80) and intra-class correlation coefficients (>0.70). The scores generated for each subscale will be transformed on a scale from 0-100, lowest to highest summary scores respectively. Participants will be asked to complete the pre-operative module of the Breast Q $\circ$  questionnaire at 2 weeks prior to the mastectomy.(APPENDIX 4) Post-operatively, they will be requested to complete the post-operative module of the Breast Q $\circ$  at 2 weeks following immediate reconstruction, as well as 6 months and 1 year following the completion of the reconstruction. (APPENDIX 5) The questionnaires will be self-administered and mailed to the participants with return envelopes and prepaid postage. To compensate our study patients for their participation, a monetary reimbursement (\$10) will be available upon completion. The Dillman method will be used to encourage patient response.

The **secondary outcomes** will include a comparison of:

1. **short and long-term complication rates**: Short-term complications are intra- and post-operative complications occurring within two months of surgery and long-term complications occur later than two-months. They will be documented and collected prospectively.

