### **9b. Intention to treat analysis**

Patients who abandon reconstruction or undergo premature explanation of either TE or implant will **not** be removed from the study and will be evaluated using the **intention-to-treat analysis**.

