### **9c. Measurement of the Primary Objective:**

#### ***i) Primary Analysis***

Each of the two domain-specific summary scores on function and satisfaction will be transformed on a scale from 0 to 100 using RUMM software. Mean scores and standard deviation for each surgery group will be calculated and compared. To address our primary aim of comparing patient satisfaction and quality of life between **Group 1** (one-stage with ADM) and **Group 2** (two-stage group without ADM) before and at the three post mastectomy follow up reference time points, we will use the **repeated measure analysis** to examine the time effect and time-group interaction. In all analyses, statistical significance will be designated at  $p <= 0.05$  level.

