### **iib-10. Sample Size**

We consider clinically relevant change in the quality of life as a difference that exceeds half a standard deviation of the baseline value. Field-testing data of the Breast Q $\odot$  has found that the standard deviation of both the psychosocial function and satisfaction distributions is approximately 20. Thus, the minimum significant difference of score in each subscale is calculated to be 10. When we set our power at 85% with a  $\beta$  error of 0.1 and a standard  $\alpha$  error rate of 0.05, and applied the equation for equal sample sizes, we calculated a **minimum sample size of 72 patients per arm** for a total sample size of 144 patients. This sample size is also sufficient with power 84%,  $\alpha$  0.05, to detect a value of 0.06 for  $\eta^2$ , representing a medium effect size of the proportion of variability in the outcome variable (Breast Q $\odot$ ) that is explained by the independent variable(s), e.g., intervention.

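### The primary repeated-measures procedure is not named; run as classical ANOVA, its natural reading, it would drop every woman missing any one of four mailed Breast Q forms

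*Combined protocol and SAP*

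**What the plan says.** Section 9c (Primary Analysis) compares the arms on two Breast Q subscales "before and at the three post mastectomy follow up reference time points", which makes four forms per woman. It uses a repeated-measures analysis "to examine the time effect and time-group interaction". Section 9a adds that covariates are handled by stratification and "controlled for during repeated measures analysis using SPSS v18". Neither section names ANOVA, a general linear model or a mixed model.

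Section iib-10 obtains 72 per arm from a 10-point difference with an SD of 20. It then adds a second check, an eta-squared of 0.06, described as "representing a medium effect size of the proportion of variability in the outcome variable".

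Section iib-8 says of the forms: "The questionnaires will be self-administered and mailed to the participants with return envelopes and prepaid postage". It also says: "The Dillman method will be used to encourage patient response". A $10 payment is offered on completion, as compensation for taking part.

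Section 9b opens "Patients who abandon reconstruction or undergo premature explanation of either TE or implant will" and goes on to say that these women stay in the study and are analysed by intention to treat. It does not mention unreturned forms. The plan gives no missing-data method, expected return rate or dropout allowance. The Study Design section has enrolment continue to 72 evaluable patients per arm and does not define evaluable.

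**The concern.** Classical repeated-measures ANOVA deletes listwise. A woman who returns three of her four forms contributes nothing to any comparison, including those at the visits she did complete. As the plan is written, an analyst could run that version and be within it.

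Two things would be at stake. The first is precision, because the 72 per arm contains no allowance for lost women. The second is the intention-to-treat aim. A woman whose reconstruction failed is promised a place in the analysis, yet one missing form would remove her. The schedule adds to this risk: section iib-8 times the two late forms from completion of reconstruction, so a woman who abandons reconstruction has no defined date for them. If the missing forms are related to how the reconstruction went, the complete cases are a selected group and the primary estimate can be biased.

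**Working it through.** **The plan's own figures.** Inputs from section iib-10: difference 10, SD 20, alpha 0.05 (taken as two-sided), power 85%.

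n per arm = 2 × (20/10)² × (1.960 + 1.036)² = 71.83, rounded up to 72. The stated figure reproduces and leaves nothing for missing forms. (The same sentence also gives a beta of 0.1. That would mean 90% power and 85 per arm; only 85% power gives 72.)

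Eta-squared check: an F test on 1 and 142 degrees of freedom with noncentrality 144 × 0.06/0.94 = 9.19 has power 85%. With noncentrality 144 × 0.06 = 8.64 it has 83%. The stated 84% lies between them. Both versions count all 144 women.

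**Complete cases under listwise deletion.** Let m be the share of forms missing at each time point. The documents give no value, so m is an assumption. Two patterns are shown:

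- The same women miss every form: complete share = 1 − m.
- Missingness is independent across the four forms: complete share = (1 − m)⁴.

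If missingness is positively correlated within women, the loss lies between the two.

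Power is for a two-sided t test at one visit, with noncentrality 0.5 × √(n/2) and 2n − 2 degrees of freedom. At n = 72 the noncentrality is 3.0 and power is 84.6%.

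| m | Same women: share, n per arm, power | Independent: share, n per arm, power |
|---|---|---|
| 5% | 95%, 68.4, 83% | 81.5%, 58.6, 77% |
| 10% | 90%, 64.8, 81% | 65.6%, 47.2, 67% |
| 15% | 85%, 61.2, 78% | 52.2%, 37.6, 57% |

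The loss is therefore 5% to 15% in the first pattern and 19% to 48% in the second.

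**What all available data would keep.** An analysis that uses every returned form keeps 72 × (1 − m) per arm at any one visit: 68.4, 64.8 or 61.2. This equals the first pattern, so the saving in women is nil when the same women miss everything and largest when missingness is scattered.

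**The case against.** The strongest reply is that the plan makes no wrong choice because it names no procedure. SPSS also fits mixed models, so naming the software settles nothing. Eta-squared is only a second check after a two-means calculation, and its 84% reproduces from a between-group F test with no repeated-measures structure. This stands to the extent that ANOVA is an inference. It is still the natural reading of the wording taken together, and nothing in the plan rules it out.

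A reader might infer that the sample will shrink by a fifth to a half. The documents do not support that. It needs an assumed 5% to 16% missing per form and independence across forms. Independence also fits poorly with a worry that particular women, those with failed reconstructions, are the ones who stop replying.

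A reader might also infer that the plan breaks intention to treat, or that failed reconstructions do drop out. Section 9b covers abandonment and explantation, not non-response. No document text says that these women return fewer forms, and the interim short-term data report a single premature expander removal. The conflict arises only if listwise deletion is used.

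Two further points stand. The power figures are for a single visit, not for the time-group test, and they credit neither analysis with the correlation between visits. The rule of 72 evaluable patients might also mean that non-evaluable women are replaced. That could preserve numbers, but not the comparison as randomized.

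**Conclusion.** The point holds in conditional form. The primary procedure and the handling of missing forms are unspecified, and the natural reading is an analysis that would discard any woman with one of four mailed forms missing. The cost cannot be fixed from the documents. At an assumed 5% to 15% missing per form, it runs from a minor loss (5% to 15% of women, single-visit power 83% to 78%) to a serious one (19% to 48%, power 77% to 57%), against 84.6% with 72 per arm. These figures assume listwise deletion, equal missing rates at all four forms and no replacement of women. The possible bias comes from which women are missing and does not depend on a particular rate.

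This goes beyond a request for detail. An analysis closer to the intention-to-treat aim is available from the same software and the same data, and it never keeps fewer women than the listwise one.

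**What to change.** State in section 9c that the primary analysis is a likelihood-based linear mixed model (SPSS MIXED, REML), fitted to the three post-operative scores on each subscale. Terms: group, visit, group-by-visit, baseline score, site and laterality, with an unstructured covariance within woman. Include every randomized eligible woman with at least one post-operative form. Say how a missing baseline score is handled, since as a covariate it would otherwise remove her.

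Report the group contrast at each of the three time points named in the primary objective, because the hypothesis claims a benefit at all of them and not at 1 year alone.

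Add a sensitivity analysis for outcome-related missingness. The mixed model is valid only if data are missing at random, and it still omits women with no post-operative form. Define evaluable, and say when the late forms fall due for a woman whose reconstruction is never completed.

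The cost is a change of SAP wording and slightly more analysis work. No extra data or software is needed.
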